**Developing Process-Specific Verbal Memory
Interventions for Veterans with TBI**

Protocol

NCT02310633

March 4, 2019

Protocol

1. Project Title: Developing Process-Specific Verbal Memory Interventions in Veterans with TBI

2. Investigator(s): [name]., [name]., [name].

3. Abstract: Memory dysfunction can result from impairments along a continuum of information processing, from poor initial acquisition of information during learning to disturbed retrieval of stored memory when it is later needed to perform a task¹. There is a critical need to better understand disease heterogeneity in order to enhance diagnosis and therapeutic management². Several subtypes of memory dysfunction after TBI have been identified^{3,4}. First, some TBI survivors exhibit impaired memory acquisition/encoding (e.g., frontal system damage)⁵. Second, some exhibit impaired memory consolidation/storage impairment (e.g., prominent damage to temporal lobe systems⁶). Third, some show impairment in retrieval of information^{5,7}. This heterogeneity results from the variable nature and severity of underlying brain trauma resulting from unpredictable mechanical forces^{2,8}. This study attempts to determine whether these subtypes of memory respond better to treatments that are focused specifically on the constituent cognitive deficit than to other treatments. There are existing training protocols for training these three components of memory processing, as follows: encoding (memory strategy training⁹), consolidation (errorless learning¹⁰), and retrieval (retrieval practice¹¹, but their efficacy has not been tested in TBI survivors with documented impairments in each component. That is, to our knowledge, there is no solid evidence for memory training in TBI survivors that supports the widely held belief that specifically matching the patient impairment to the treatment leads to better treatment outcomes. This project attempts to fill this gap in our knowledge. In an alternating treatments design, TBI survivors with encoding, consolidation, or retrieval deficits will undergo (a) a treatment matched to their deficit and (b) a treatment that addresses a different deficit. High resolution imaging and neurocognitive biomarkers will be used to predict response to treatment. Results will be used as a basis for a larger clinical trial of memory rehabilitation in brain injured populations.

4. Background:

Traumatic brain injury (TBI) has emerged as a “signature injury” of the OIF-OEF-OND combat experience. Enduring cognitive deficits after TBI present barriers to full recovery and re-entry into societal roles, with executive dysfunction, poor attention-concentration, and memory difficulties being the most persistent disabilities faced by TBI survivors¹².

Current Knowledge. There is considerable heterogeneity in the nature and severity of memory disorders after moderate-severe TBI(M-STBI)⁸, resulting not only from variability in severity and etiology of TBI, but also from variable loci of neuroanatomic damage¹³. Chronic episodic memory deficits after M-STBI are often rooted in deficient encoding and/or consolidation of to-be-learned information^{5,14}, or from retrieval deficits associated with frontal-executive damage⁴. Meta-analytic reviews of memory rehabilitation studies show that memory strategy training may improve TBI-related memory deficits of any severity, leading to its recommendation by ACRM as a practice standard¹⁵. More limited data on errorless learning (EL), which rebuilds learning/memory skills in a way that prevents errors, suggests that EL is a promising approach to treating severe memory deficits^{10,16,17}. Retrieval practice (in which participants practice the act of retrieving information with appropriate cueing and support) improves paired-associate

learning in the TBI population^{18,19}. Other memory therapies with promising but unproven efficacy in RCT's include spaced retrieval^{20,21} and the method of vanishing cues^{22,23}.

Gaps in Knowledge. Although these protocols may lead to improved learning and memory after M-STBI, little is known about their mechanism(s) of action or whether they would be differentially effective in TBI survivors with deficits at different stages of the memory process. There have been no comparative effectiveness studies involving these treatments, and no group studies have attempted to match patients to treatments that specifically target the locus of memory impairment in encoding, consolidation, or retrieval. If, in fact, some patients suffer from consolidation failure⁶, while others have prominent encoding or retrieval deficits^{5,24,25}, it is likely that alternative memory interventions, each matched to the patient's primary deficit, may be needed to maximize individual rehabilitation outcomes. Stage of recovery/time since injury may also be important, as encoding deficits and consolidation deficits recover differentially in severely injured patients, with poor encoding representing the more enduring problem¹³.

Relevance: Managing and alleviating residual effects of traumatic brain injury is a key priority area and represents a critically important public health problem facing the veteran population. Differential efficacy of specific rehabilitation programs may be an important factor for clinicians to consider when offering health services to veterans with cognitive impairment.

Benefit to Veterans. A better understanding of the efficacy of memory rehabilitation may provide clinicians with better decision-making support for prescribing different available therapies to alleviate TBI-related cognitive and memory dysfunction. Better understanding of individual differences in TBI-related memory dysfunction, and of underlying structural and functional brain dysfunction may also explain the neural basis for heterogeneous memory difficulties veterans suffer after M-STBI.

5. Specific Aims:

Aim 1. Aim 1 is to refine and validate three separate, process-specific memory rehabilitation treatments that focus on improving information-processing at the encoding, consolidation, or retrieval stage for Veterans with chronic moderate/severe TBI.

Objective 1.1. Generate treatment manuals for three process-specific memory treatments.

Objective 1.2. Test and refine treatment fidelity so that each of the three interventions can be reliably delivered by different clinicians.

Aim 2. Aim 2 is to provide a preliminary test of the response to the three memory interventions. At baseline, TBI survivors will be evaluated for memory function in each of these three memory component processes using established neuropsychometric methods. Their experimental treatment allocation will be to the treatment targeting their most impaired memory component. In addition, each subject will serve as his/her own control, by engaging in a treatment targeted to another memory component ('mismatched' group).

Hypothesis A. The matched vs. mismatched group will show differential improvement in memory component function, with the former group benefitting to a significantly greater degree. (Primary measures: Memory component performance, encoding, consolidation, retrieval; secondary: cognitive function and quality of life).

Aim 3. Aim 3 is to establish links between the behavioral taxonomy of the three memory components and differences in brain structure and function documented with diffusion tensor imaging and functional connectivity analysis. This is a key first step in establishing brain-based metrics of neuroplastic change after memory therapy in our research program.

Objective 3.1. Identify specific and unique imaging signatures that distinguish patients with deficits in encoding, consolidation, and retrieval, respectively. Primary measures: structural measures of morphometry and white matter integrity (FA) and functional connectivity (cross correlation and total interdependence) in identified brain networks damaged in TBI.

Clinical Implications. This research has the potential to devise a method to match specific

subcomponents of memory impairment to specifically targeted memory interventions, thus maximizing recovery of memory and function. The results of this investigation will be used to refine the interventions, to evaluate cognitive and functional endpoints, and to power a larger clinical trial that will yield data enabling clinicians to match TBI patients to effective treatments based on their individual profile of memory dysfunction.

6. Research Plan:

6.1. Study Design. The proposed research will be conducted in three phases: Intervention Development, Patient Characterization and Classification, and Initial Testing of Treatment Efficacy.

6.2. Phase 1: Intervention Development. During the first 6 months of the project, we will formalize, manualize, and perform preliminary fidelity testing on three memory interventions targeting process-specific memory deficits after TBI in Veterans: (a) memory strategy training (to boost encoding), (b) errorless learning (to improve consolidation, and (c) retrieval practice (to rehabilitate deficits in retrieval).

6.2.1. Materials Common to Memory Interventions. Each of the three treatment conditions will utilize the same training materials, a set of verbal paired-associates (VPA) and a set of face-name pairs (FNP), both presented for training in associative learning. Each session will involve training utilizing two 12-item VPA lists and two sets of 12 FNP's, for an overall total of 144 unique VPAs and 144 FNPs. The VPA's are weak paired associates^{26,27} (have a forward association strength of <.01²⁸), and that do not contain words from clinical memory tests given in Phase 2. FNP's are constructed by pairing face-front black and white photographs from Stringer's Ecologically-Oriented Neurorehabilitation of Memory (EON-MEM) protocol²⁹. Training stimuli will be presented on a desktop computer using E-prime software.

6.2.2. Memory Strategy Training (MST). MST, in which persons with brain injury are taught specific strategies useful for encoding new information at the point of learning, is a widely used rehabilitative technique^{9,30,31} that is an *ACRM practice standard*¹⁵. While specific strategies vary across studies, most teach the participant to form meaningful cognitive associations between memoranda through the use of imagery or semantic encoding, building a form of memory encoding known as relational memory³². Relational encoding, a key process that enhances the strength and durability of episodic memory^{33,34}, can be reduced or impaired after TBI³⁵. Successful relational memory involves two distinct mnemonic mechanisms: the generation of an association between to-be-encoded items (a frontal/executive function)^{36,37} and the binding of that association into a cohesive memory trace (a function of the hippocampal memory system)^{33,38}. MST may be particularly useful in enhancing the first of these two processes.

6.2.2.1. Procedure. Six biweekly sessions of MST will be conducted. Two VPA lists and two FNP lists will be used in each session. During MST, VPAs (e.g., "candle-table") or FNPs will be presented in horizontal arrangement on a computer screen at a rate of 1 per 6 seconds (this may be modified based on participant processing speed). For **VPA learning**, participants will be asked to generate a memorable sentence (first list) or form a distinctive mental image (second list) that links the two VPA items together. The therapist will help the participant generate sentences and images that are distinctive or unusual, and therefore more memorable. Specific examples of distinctive sentence-based and imagery-based encoding will be given (e.g., "The wax from the candle poured onto the table", or an image of a candle scorching a table) and will be developed as the treatment is manualized. Immediately following list presentation, the cue word will be presented without the target (e.g., "candle-_____") and the participant will be asked to generate the target. Spontaneous production of targets will be recorded. For each item not spontaneously recalled, participants will be asked to retrieve the

sentence (first list) or image (second list) that they created during encoding, and will then be asked to retrieve the target word again. Unsuccessful retrieval will be initially cued by the therapist. Prompted recall will also be recorded. This procedure will be repeated five times for each list, each followed by a retrieval phase. For each session, the dependent measure is the percentage of correct target words (out of 12) in spontaneous and cued recall for each list during the final exposure trial. For **FNP learning**, we will use a training approach adapted from Hampstead³⁹ and Stringer⁹. Training teaches patients to self-generate cues linking faces and names; patients will also be provided cues to standardize procedures and to encourage strategy development. For each FNP, participants will be directed to a salient facial feature (a visual cue like a long nose) and given a nickname that rhymes with the actual name (verbal cue) linking the feature to the name. Patients will be instructed to associate the visual and verbal cues by creating mental images that emphasize or exaggerate the relationship between cues. After initial learning, FNP's will be repeated five times. On each presentation, participants will be asked to recall the visual cue, then the verbal cue, and then finally the name. Dependent measure is the percent correct recall of visual cues, verbal cues, and names on the final trial of each list.

6.2.3. Errorless Learning (EL). EL refers to a group of techniques that promote recovery of memory abilities using procedures that explicitly prevent the patient from making errors during learning¹⁰. EL is based on the premise that errors during training become primed in long term memory via implicit memory mechanisms relatively spared in amnesia⁴⁰. Because of impairment in explicit memory consolidation that would normally provide corrective influence, these errors exert an unusually strong detrimental effect on relearning. While the standard interpretation of EL is that implicit memory is responsible for the treatment effect^{41,42}, it has been more recently shown that the EL advantage results from residual, though impaired, episodic memory consolidation due to temporal lobe damage^{43,44}. EL has been shown to be a promising tool in memory rehabilitation^{15,40,45}, at least for individuals without severe executive deficits⁴⁶.

6.2.3.1. Procedure. Six biweekly sessions of EL will be conducted, each using two VPA lists and two FNP lists. During EL, the word pairs (e.g., "candle-table") or face-name pairs will be presented in horizontal arrangement on a computer screen at a rate of 1 per 6 seconds with no encoding instructions. After initial presentation, the cue will be presented without the target. For VPA learning, the cue word in each pair ("candle - _____") will be presented, and the participant will be asked to provide the second (target) word, ***but only if they are certain they can retrieve it accurately. Guessing is explicitly discouraged.*** If the participant cannot provide the word within 3 seconds, the word appears on the screen for 3 seconds and the participant is asked to read the pair aloud. During training, each list will be presented five times in this fashion. The dependent measure is the percent correct target words produced (out of 12) during the fifth exposure trial for each list. The procedure will be repeated for the second VPA list and then for the two FNP lists, yielding 4 accuracy measures (percent correct) for each session.

6.2.4. Retrieval Practice (RP). Some authors have argued that practicing retrieval during learning is an essential feature of successful learning^{10,47}. Effects of RP are most robust when retrieval is effortful, successful and spaced over time^{48,49}. If retrieval of a learned item is practiced shortly after it is learned, but before it is forgotten, subsequent recall is enhanced, a phenomenon known as the "testing effect"⁴⁷. RP has been used recently to improve performance of memory-impaired patients with multiple sclerosis⁵⁰ and M-STBI^{11,19}.

6.2.4.1. Procedure. Six biweekly sessions of RP will be conducted. We will follow procedures outlined in Sumkowski et al¹⁹, who demonstrated efficacy of RP in a small group of patients with M-STBI and chronic memory deficits. For each session, two sets of 12 VPA's and 12 FNP's will be used. Paired stimuli will be presented together for 6s on a computer screen, and the participant will be asked to read the VPA or say the name (FNP) aloud. Following this, 3 6s filler pairs (other VPA's or FNP's) will be presented. Then, a 5s cued

recall test (candle-_____), followed by a 1-s feedback screen (candle-table) will be presented, followed by another six 6s filler trials and another 5s cued recall test and 1s feedback. This continues until all 12 VPA's or FNP's are given. After VPA is complete, FNP is administered (counterbalanced). After a brief delay, the participant completes two separate delayed cued recall tests (VPA, FNP, counterbalanced). The procedure is repeated for the second set of VPA's and FNP's. Dependent measure: Percent correct scores on the delayed recall test for each of the two VPA and two FNP sets, recorded each session.

6.2.5 Manualization and Fidelity Testing. During Phase 1, session-by-session procedures, including instructions to therapists and patients, stimuli and stimulus presentation schedules, methods of data collection, and permissible procedural variations will be formalized into a treatment manual for each of the three interventions. Six Master's level therapists will be trained in all three interventions, and will practice administering them to volunteer participants. At the end of Phase 1, each therapist will administer each treatment to a Veteran participant with M-STBI. Each session will be video recorded for evaluation of treatment fidelity by the study team^{51,52}, which will review session recordings and will rate the degree to which the therapist adhered to the following aspects of the protocol: communication of content to the participant (consent, rationale for treatment, instructions for engaging in training), accurate use of cues, selection of stimulus materials, recording of data, and adherence to designated treatment schedules. We will develop a rating sheet that provides feedback to therapists on their adherence to the manualized protocol⁵³.

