## 2.6. Statistical Analysis Plan

The procedure for classifying participants into Encoding, Consolidation, and Retrieval groups is outlined in Section 2.3.2. It is recognized that, although patients will be classified according to their primary memory deficit, some may have relevant impairment in more than one domain. For this reason, each participant will be given a composite score for encoding, consolidation, and retrieval, and all three of these composite scores will be used in exploratory analyses of predictors of treatment response. Phase 2 neuropsychological scores (z-score transformed data using appropriate age- and education corrections) and neuroimaging data (NEW, FA, diffusivity measures, morphological volumes, TI from RS-fMRI for specific ROI pairs) will be analyzed using 1-way (Group: Encoding, Consolidation, Retrieval) ANOVAs followed by pairwise follow-ups with the Tukey HSD test. Dependent variables used to evaluate memory performance in Phase 3 are detailed in Section 2.2 above, and include session-wise percent correct data on VPA and FNP memory probes as well as post-treatment and 1-month follow-up probes. Data from Phase 3 will be analyzed by comparing effect sizes of matched and unmatched treatments at the individual subject level using methods described by Parker et al. These measures include (a) percentage of non-overlapping data points, (b) quantitative measures of improvement rate and difference level, and (c) Tau-U, a nonparametric measure of effect size that tests for differences in two treatments after trend adjustment. Additional measures will also be explored, including interrupted time-series/regression approaches and the last-day-of-treatment comparison approach. We will also evaluate the separate influence that severity of memory deficit has on treatment response (independent of patient grouping) by performing hierarchical linear regression in which severity is coded as average z-score on memory indices derived from phase 2, and patient grouping is dummy-coded.

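### Hypothesis A names encoding, consolidation and retrieval as primary, but the visible SAP analyses VPA/FNP percent correct, scored differently by treatment and compared only within individuals

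*Protocol*

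**What the plan says.** Protocol Section 5 (Aim 2, Hypothesis A) predicts differential improvement in memory component function between matched and mismatched treatment, "with the former group benefitting to a significantly greater degree". It lists the outcomes as "Primary measures: Memory component performance, encoding, consolidation, retrieval; secondary: cognitive function and quality of life".

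SAP Section 2.6 gives each participant a composite score for each component and says that "all three of these composite scores will be used in exploratory analyses of predictors of treatment response". The Phase 3 dependent variables are different: they "include session-wise percent correct data on VPA and FNP memory probes as well as post-treatment and 1-month follow-up probes". The analysis consists of "comparing effect sizes of matched and unmatched treatments at the individual subject level", using non-overlapping points, "quantitative measures of improvement rate and difference level", and Tau-U. No pooled matched-versus-mismatched contrast is stated.

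The session scores are set out by treatment in Protocol Sections 6.2.2.1, 6.2.3.1 and 6.2.4.1:

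- **Memory strategy training (MST), VPA:** "percentage of correct target words (out of 12) in spontaneous and cued recall for each list during the final exposure trial". Uncued recall is kept separately: "Spontaneous production of targets will be recorded".
- **MST, FNP:** visual cues, verbal cues and names on the final trial.
- **Errorless learning (EL):** targets produced on the fifth exposure, with guessing discouraged.
- **Retrieval practice (RP):** a separate delayed cued recall test.

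Under Section 6.4.2 and Table 4, each of 12 participants receives one matched and one mismatched treatment, six sessions each.

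**The concern.** There are two linked problems.

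First, the stated primary measure and the analysed outcome differ. The composites are built for Phase 2 classification (Protocol Section 6.3.2.2) from CVLT features. The CVLT-II is in the pre-treatment battery (Table 1) and not among the measures repeated after treatment (Table 5). All three treatments train on the same VPA and FNP materials. A gain on those tasks would therefore support better learning of the lists under matched treatment, but would not by itself show which memory component improved. The protocol intends the results to help power a larger trial, so the quantity estimated needs to be clear.

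Second, a participant's matched and mismatched scores come from different treatments and, in part, from different kinds of test. At the individual level, any general difference between the treatments or their scoring can look like a matching effect or hide one.

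**Working it through.** **1. The design figure.** Table 4 has 3 deficit groups with 4 orders each and one participant per order: 3 × 4 = 12, as stated. Coding MST = 1, EL = 2, RP = 3, the orders are Encoding 12, 13, 21, 31; Consolidation 21, 23, 12, 32; Retrieval 31, 32, 13, 23. Each treatment is matched for 4 participants and mismatched for 4. The matched treatment comes first for 6 of 12.

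**2. How far the scores differ.** Scores per session are:

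- MST: 2 VPA lists × 2 scores + 2 FNP lists × 3 scores = 10
- EL: 4
- RP: 4

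MST spontaneous VPA recall and EL recall are close to comparable. The clear departures are RP's delayed test and MST's cued and FNP cue scores. RP appears in 8 of the 12 orders.

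**3. Effect of a pure scoring offset.** Assume no matching effect and RP scores 10 points lower for everyone. With D = matched minus mismatched, in the order listed above:

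- Encoding: 0, +10, 0, +10
- Consolidation: 0, +10, 0, +10
- Retrieval: −10, −10, −10, −10

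Four participants show +10, four show −10 and four show 0. The mean is (40 − 40)/12 = 0. The offset is fully confounded with matching in eight individual comparisons and cancels in the balanced average.

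**4. What this does to individual effect sizes.** Take 6 versus 6 independent normal session scores, a 10-point shift and no trend. Expected Tau is 2Φ(10/(SD√2)) − 1; the percentage of non-overlapping points is by simulation.

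| Session SD (assumed) | Tau, no trend adjustment | Non-overlapping points |
|---|---|---|
| 5 | 0.84 | 73% |
| 10 | 0.52 | 41% |
| 20 | 0.28 | 26% |
| No offset | 0 | 14% |

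These are illustrations, not values of the planned Tau-U, which adjusts for trend. A slope across sessions is unchanged by adding a constant to every session, so improvement rate is free of a constant offset.

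**5. The pooled contrast.** Regress D on an intercept (the matching effect), period (+1 if matched came first, −1 if second) and treatment (two terms, each equal to 1 if that treatment was the matched one, −1 if the mismatched one, otherwise 0). In X′X the intercept has 12 on the diagonal and 0 in every cross-term. The intercept is therefore simply the mean of D; period and treatment terms change only the residual variance and df.

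- SE = SD/√12 = 0.289 residual SD
- df = 12 − 4 = 8, t = 2.306
- 95% CI half-width = 2.306 × 0.289 = 0.67 residual SD, or 6.7 to 13.3 points if that SD is 10 to 20 (assumed)
- Difference detectable with 80% power at two-sided 5% (both assumed): about 0.92 residual SD

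**6. What pooling does not remove.** If RP scoring costs 20 points in one deficit group and 10 in the other two, the offset no longer cancels:

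- Extra cost in the retrieval group, where RP is always the matched treatment: −10 × 4/12 = −3.3 points
- Extra cost in the encoding or consolidation group, where RP is mismatched for 2 of 4: +10 × 2/12 = +1.7 points

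Such an interaction is plausible: Section 6.3.2.2 describes the consolidation type partly by rapid forgetting, which a delayed test would expose.

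**The case against.** **Unseen text.** SAP Section 2.6 refers to Sections 2.2 and 2.3.2, which were not available. Protocol Section 6.4.2 calls VPA/FNP performance a proximal outcome and sets it beside the secondary outcomes, so it may be the intended working version of the primary measure. This stands as a limit: the unseen sections could supply the mapping to components. The scoring of the post-treatment and 1-month probes is not shown either, so the scoring point applies to the session scores only.

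**Pilot and single-case design.** Individual effect sizes suit an alternating treatments design, and Aim 2 calls this a preliminary test. That is right, and the single-case methods are not the fault. However, Hypothesis A is worded as a significantly greater benefit, and the regression approaches in Section 2.6 are only to be explored, with no matched-versus-mismatched term stated.

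**Level or rate.** Hypothesis A concerns improvement, and Section 6.4.2 expects differences in both elevation and slope. A pooled contrast on the session mean alone would rest on the offset-sensitive quantity. This is correct, and both should be reported.

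**Stronger readings.** A reader might infer that an identically scored outcome would need extra testing. It would not: Section 6.5 and Table 5 already schedule the RAVLT, BVMT-R and EON-MEM simulations before treatment, after each treatment and at 1 month, and nothing there makes them differ by treatment. A reader might also take the Tau figures as predictions for this trial. The documents give no offset, direction or SD to support that.

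**Conclusion.** The concern holds on the visible text. The primary measures named in Hypothesis A are not the Phase 3 outcomes in SAP Section 2.6, and the outcomes used there are scored differently by treatment. In individual level and non-overlap comparisons, a treatment or scoring offset is confounded with matching. Improvement rate escapes a constant offset. Averaging over the 12 participants cancels any offset that is equal across deficit groups, but the SAP states no such average.

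The real size of any offset is unknown; the 10 points and the SDs of 5 to 20 are assumptions. The documents do not support concluding that Phase 3 is uninformative or that the single-case analysis should be dropped. The changes should be made before analysis. Confidence is medium because part of the SAP could not be read.

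**What to change.** 1. **Restate the claim.** Word the Hypothesis A primary measure and conclusion as matched-versus-mismatched learning on the VPA and FNP tasks, unless SAP Sections 2.2 or 2.3.2 map these to the components. If they do, cite that mapping in Section 2.6.
2. **Name the most comparable score.** Use target words or names only, with MST spontaneous recall, and leave out cued and visual/verbal-cue scores. Report VPA alone as a check, because MST names are asked for after the cues. State that RP remains a delayed test, so individual comparisons involving RP stay offset.
3. **Add one pooled contrast.** Report the mean matched-minus-mismatched difference over the 12 participants, with 95% CI, for both the six-session mean and the improvement rate. Say in advance whether period and treatment terms are included. Keep Tau-U and the other individual effect sizes as descriptive.
4. **Check it on identically scored measures.** Report the same contrast, as change over each treatment period, on the RAVLT, BVMT-R and EON-MEM simulations. Keep these secondary and do not read them as component scores.
5. **State the limit.** A scoring-by-deficit interaction stays in the VPA/FNP contrast.

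The cost is wording in the protocol and SAP and a few added analyses of data already planned. The primary claim becomes narrower, and the pooled estimate is imprecise at 12 participants.
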